3.1. Sample Size

A sample size of 20 subjects randomized per treatment group was chosen in light of logistical needs and so as to accumulate sufficient safety data on NGM282. The associated power to detect a treatment difference in the primary efficacy analysis, for either NGM282 comparison versus placebo, is at least 90%, based on the following assumptions:

A. ALP Population Mean Change from Baseline:

	NGM282 (either 1 mg or 3 mg)		Placebo
Subjects taking UDCA at Baseline	-75	0	
Subjects not taking UDCA at Baseline	-475	0	

- B. Equal numbers of completing subjects for each of the four cells above
- C. Population (not sample) standard deviation (SD) between subjects within each of the four cells above: 200
- D. Analysis of variance with treatment, UDCA (yes/no), treatment with UDCA (all as classification variables), and Baseline value (as a continuous covariate) in the model
- E. 20% dropout rate, from randomization to Week 12, yielding 16 completing subjects per treatment group
- F. Dunnett's 1-step adjustment for multiplicity, requiring a type 1 error rate of 0.027 (2-sided) for each comparison versus placebo

Assumptions underlying the means and SDs are based on studies evaluating UDCA as a first-line therapy and in studies where secondary or combination therapies with UDCA have been utilized. The power in the primary efficacy analysis may be slightly higher, since it incorporates Dunnett's step-down adjustment and utilizes repeated measures to reduce the power losses due to dropouts. On the other hand, power may decrease slightly, to the degree that unequal numbers of subjects are randomized taking and not taking UDCA. In addition, the probability that the observed least square (LS) mean treatment difference exceeds 30% of the placebo LS mean change has not been examined.

To randomize 60 subjects, approximately 90 will be screened.

If, in contrast, the population SD is 300, the power is roughly 81% for each NGM282 comparison versus placebo.

3.2. Randomization, Stratification, and Blinding

At Day 1, all eligible subjects will be randomized [REDACTED] to one of the three treatment arms (NGM282 1 mg, NGM282 3 mg, or placebo) in a 1:1:1 ratio. The randomization will be stratified by ursodeoxycholic acid (UDCA) use (yes/no), to ensure an even distribution across the three treatment groups. The determination of the status will be based on the medical history and the concomitant medications history at randomization.

The unmasking of a subject's treatment will be available to the Principal Investigator (PI) in the event of a medical emergency or an AE that necessitated identification of the study drug for the welfare of that subject. Except for the medical emergency, the PI and clinic staff will remain blinded during the conduct of the study and until all discrepancies in the clinical database are resolved and the database is locked. The date and time when the PI removed the study blind for an individual subject will be documented [REDACTED] and an automated notification will be sent to the Sponsor. However, all attempts should be made to contact the Sponsor prior to unblinding. The contracted CRO's pharmacovigilance team may also be required to break the blind in the case of a medical emergency.

3.3. Analysis Sets

3.3.1. Randomized Set

All randomized subjects will be included into the Randomized Set. All subjects in the Randomized Set will be grouped according to the randomized treatment even if this differs from the actual treatment received.

3.3.2. Safety Set

All randomized subjects who receive at least one dose (full or partial) of study drug and have at least one post-dose safety evaluation will be included in the Safety Set. In analyses using this set, subjects will be grouped according to actual treatment received if this differs from the randomized treatment.

3.3.3. Full Analysis Set

All randomized subjects who receive at least one dose (full or partial) of study drug and have at least one valid, non-missing post-dose efficacy/PD parameter value will be included in the Full Analysis Set (FAS). This will be the set for the primary analyses of efficacy and PD endpoints. In FAS analyses, subjects will be grouped according to randomized treatment if this differs from actual treatment received.

4. Subject Disposition

4.1. Disposition

Subject disposition will be summarized for the randomized Set. A summary of the analysis sets includes the number and percentage of subjects for the following categories: subjects randomized, subjects who completed treatment, subjects who completed the study, subjects who discontinued

from the study, subjects in Safety Set, subjects in the FAS Set, subjects in the PP Set, and subjects in the pharmacokinetic Set. All percentages will be based on the number of subjects randomized.

Primary reason for treatment discontinuation and primary reason for study discontinuation will be summarized in the disposition table. Reasons for study discontinuation include the following: adverse event, death, lost to follow-up, trial screen failure, withdrawal of consent by subject, subject refused to return for follow-up visit, other.

A listing to subject disposition data will be presented for each subject, including enrollment date, treatment start date, treatment end date, treatment discontinuation reason and study discontinuation reason.

4.2. Protocol Deviations

The protocol deviations/violations will be identified and assessed by clinical research physician or designee following institution standard operational procedures. All protocol deviations will be summarized using the FAS. Protocol deviations will be presented in a listing.

5. Demographics and Baseline Characteristics

5.1. Demographics

A summary of demographic and baseline information will be presented for the Randomized Set, FAS and Safety Set. The demographic characteristics consist of age (years), sex, race, and ethnicity. The Baseline characteristics consist of Baseline height (cm), Baseline weight (kg), and Baseline body mass index (BMI) (kg/m²). Body mass index is calculated as (body weight in kilograms) / (height in meters)².

A subject's age in years is calculated using the informed consent date and date of birth. Age (years), Baseline height (cm), Baseline weight (kg), and Baseline BMI (kg/m²) will be summarized using descriptive statistics. The number and percentage of subjects by sex (Male, Female), race (White, Black or African American, Asian, American Indian or Alaska Native, Native Hawaiian or Other Pacific Islander, and Other), and ethnicity (Hispanic or Latino, Not Hispanic or Latino) will also be reported. Percentages will be based on the total number of subjects in the Randomized Set, FAS or Safety Set, as applicable.

Subject demographic and Baseline characteristics will be presented in a listing.

5.2. Baseline Disease Characteristics

A summary of Baseline disease information will be presented for Randomized, FAS and Safety Set. The Baseline disease characteristics consist of UDCA use and duration of PSC (years).

Duration of PSC in years is calculated as (the informed consent date - date of diagnosis of PSC + 1)/365.25. It will be analyzed using descriptive statistics. If the date of diagnosis of PSC is completely or partially missing, the following imputation rules should be utilized in the analysis:

- If year, month, and day are missing then use the earlier of the patient's first visit date or the consent date.

- If either month or month and day are missing, use January 1.
- If only day is missing, impute the first day of the month.

UDCA use (yes/no) will be summarized by number and percentage of subjects. Percentage will be based on the total number of subjects in the Randomized, FAS or Safety Set, as applicable.

Subject Baseline disease characteristics will be listed.

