4 STUDY DESIGN

This is a multiple-center, randomized, double-blind, placebo-controlled, parallel-group study of NGM282 when administered for 12 weeks as a daily subcutaneous (SC) injection in patients with PSC. Approximately 60 subjects will be randomized across approximately 40–45 sites worldwide.

Patients will sign the Informed Consent Form at or prior to the Screening Visit and will undergo screening assessments to verify eligibility for the study (up to 6 weeks). Patients to be studied will have confirmed PSC as defined by an elevated ALP and either liver histology or cholangiography consistent with PSC. The presence of IBD is allowed as well as treatment with a stable regimen of biologic, immunosuppressant, or systemic corticosteroid therapy. UDCA therapy is allowed at stable doses for at least 12 weeks and < 27 mg/kg/day. Patients with decompensated cirrhosis, cholangiocarcinoma (diagnosed or suspected), acute cholangitis, or recently placed bile-duct stents will be excluded from this study. All subjects with concomitant IBD will be required to have had a colonoscopy within 12 months of Screening with no evidence of dysplasia. All subjects will undergo MRCP at Screening.

On Day 1, subjects will be randomized into one of the three treatment arms (NGM282 1 mg, NGM282 3 mg, or placebo) in a 1:1:1 ratio. The randomization will be stratified according to concurrent UDCA or no-UDCA status to ensure an even distribution across the three groups. Study-drug SC self-administration instructions and training will be provided to the subjects and a weekly study-drug kit will be dispensed. Treatment assignment will be blinded to the sites, subjects, Sponsor, and Medical Monitor throughout the study period.

The first dose (Day 1) and doses at Weeks 1, 2, 4, 8, and 12 will be self-administered in the clinic, with all other doses through Week 12 self-administered at home. Self-administration should occur at approximately the same time in the morning for every dose in both the clinic and at home.

Subjects will return to the clinic on Weeks 1, 2, 4, and 8 for on-treatment assessments and to receive weekly study-drug kits. Week 12 will be the End of Treatment (EOT) clinic visit. Subjects will return to the clinic at Week 16 (or 4 weeks after last dose) for an End of Study (EOS) follow-up visit.

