5 SUBJECT SELECTION

5.1 INCLUSION CRITERIA

Patients who meet the following criteria may be included in the study:

1. Males and females between 18 and 75 years of age inclusive who are able to comprehend instructions and follow the study procedures, and are willing to sign an Informed Consent Form (ICF).
2. Confirmed diagnosis of PSC based any **two** of the following three criteria:
 - a. Historical evidence of an elevated ALP > ULN from any laboratory
 - b. Liver biopsy consistent with PSC
 - i. Patients with small-duct PSC on liver biopsy must also have a concurrent diagnosis of IBD
 - c. Abnormal cholangiography consistent with PSC as measured by MRCP, ERCP, or percutaneous transhepatic cholangiography
3. Subjects must have certain additional laboratory parameters in specified ranges at Screening, as follows:
 - a. ALP > 1.5 × ULN
 - b. Total bilirubin ≤ 2.5 mg/dL
 - c. ALT and AST < 5 × ULN
 - d. Serum creatinine < 2 mg/dL or creatinine clearance > 60 mL/min by Cockcroft-Gault calculation
 - e. Platelets ≥ 100 K/uL
 - f. International Normalized Ratio (INR) ≤ 1.3 (in the absence of warfarin or other anticoagulant therapy)
 - g. Carbohydrate antigen 19-9 (CA19-9) ≤ 130 U/mL
 - i. Patients with a CA 19-9 > 130 U/mL may be enrolled if they have two results a minimum of 4 weeks but not greater than 1 year apart and not more than 50 U/mL difference between the two results
4. Patients taking UDCA will be allowed to enroll if meeting the following criteria:
 - a. Total daily dose of < 27 mg/kg/day
 - b. Minimum of 12 weeks of treatment
 - c. No significant dosage changes during 8 weeks prior to Screening
 - d. Minimum of 12-week washout period prior to Screening if UDCA is stopped

5. Patients with concomitant IBD are allowed to enroll upon meeting the following criteria:
 - a. A colonoscopy within 12 months of Screening with no evidence of dysplasia
 - b. No episode of an IBD flare or IBD flare-related bloody diarrhea within 6 months of Screening and through Day 1
 - c. Stable regimen of biologic treatments, immunosuppressive, or systemic corticosteroids (< 10 mg/day) for > 12 weeks prior to Screening and through Day 1
 - i. Vedolizumab is an excluded biologic treatment
6. Female patients are eligible for the study if they meet the following criteria:
 - a. Are not pregnant or nursing

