10.5 INFORMED CONSENT

This study will be conducted in compliance with ICH E6 Good Clinical Practice: Consolidated Guidelines pertaining to informed consent. At the first visit, prior to initiation of any study-related procedures, patients must give their written consent to participate in the study after having been informed about the nature and purpose of the study, participation/termination conditions, and risks and benefits. The informed consent document must be signed and dated by the patient and PI, or designee, prior to study participation. A copy of the informed consent document must be provided to the subject. Signed consent forms must remain in the subject's study file and be available for verification by Sponsor or its representative at any time.

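### SAP 5.2 turns a completely unknown PSC diagnosis date into a disease duration of about one day, which understates mean duration in the baseline table and hides the missing data

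*SAP*

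**What the plan says.** SAP 5.2 names two baseline disease characteristics, UDCA use and duration of PSC, and summarises them for the Randomized Set, FAS and Safety Set. The formula is: "Duration of PSC in years is calculated as (the informed consent date - date of diagnosis of PSC + 1)/365.25". On how the variable is used: "It will be analyzed using descriptive statistics". SAP section 3 defines those statistics as n, mean, standard deviation, median, minimum and maximum.

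For incomplete diagnosis dates the section states that "the following imputation rules should be utilized in the analysis", so imputed dates feed the tables. There are three rules:

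- Nothing known: "If year, month, and day are missing then use the earlier of the patient's first visit date or the consent date".
- Only the year known: 1 January of that year.
- Only the day unknown: the first of the month.

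The order of consent and first visit comes from the protocol. Section 4 says: "Patients will sign the Informed Consent Form at or prior to the Screening Visit". Section 10.5 says: "At the first visit, prior to initiation of any study-related procedures, patients must give their written consent".

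**The concern.** An imputation rule for a descriptive variable should give a plausible value or leave the value missing. This one does neither. It gives a subject whose diagnosis date is wholly unknown a duration close to zero, as if the diagnosis had been made on the day of consent.

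That is implausible for many eligible subjects. Protocol 5.1 requires any two of three diagnostic criteria, and one of them is "Historical evidence of an elevated ALP > ULN from any laboratory". For patients taking UDCA it also requires: "Minimum of 12 weeks of treatment". The other two rules work in the opposite direction: they take the earliest date compatible with what is known and so lengthen duration.

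At stake is the accuracy of one row in the baseline table. The mean is pulled down, the minimum can become an artefact, and n looks complete although some durations are unknown.

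**Working it through.** The plan states no figure for this item, so there is nothing to reproduce. The check puts the imputed date into the SAP's formula and follows the result into an arm mean.

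**Step 1: which date is imputed.** Consent falls on or before the Screening Visit (Protocol 4 and 10.5), so the earlier of first visit and consent is the consent date.

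**Step 2: the resulting duration.** (consent − consent + 1)/365.25 = 1/365.25 = 0.0027 years, that is, 1 day.

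If a first visit preceded consent, contrary to the protocol, the value would still be small:

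- 14 days earlier: (14 + 1)/365.25 = 0.041 years.
- 42 days earlier, the whole screening window: (42 + 1)/365.25 = 0.118 years.

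For comparison, a diagnosis 12 weeks before consent (the minimum prior treatment for UDCA users) gives (84 + 1)/365.25 = 0.233 years.

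**Step 3: the partial-date rules.** The largest overstatement is about 364/365.25 = 1.0 year when only the year is known, and 30/365.25 = 0.08 years when only the day is missing. These errors are bounded. The error from the fully missing rule is nearly the whole of the true duration.

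**Step 4: effect on an arm mean.** Inputs:

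- n = 20 randomised per arm (SAP 3.1).
- k = fully missing dates in the arm. Not in the documents; 1, 2 and 4 are assumed.
- D = true mean duration in years. Not in the documents; 3, 5 and 10 are assumed.
- Subjects with missing dates are assumed to have the same true mean as the rest.

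Tabulated mean = [(n − k) × D + k × 0.0027]/n, so bias = −(k/n) × (D − 0.0027), or about −(k/n) × D.

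| k of 20 | Relative bias | D = 3 | D = 5 | D = 10 |
|---|---|---|---|---|
| 1 | −5% | −0.15 | −0.25 | −0.50 |
| 2 | −10% | −0.30 | −0.50 | −1.00 |
| 4 | −20% | −0.60 | −1.00 | −2.00 |

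Example: k = 2, D = 5 gives (18 × 5 + 2 × 0.0027)/20 = 4.50 years.

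**Step 5: other statistics in the row.** One imputed subject sets the minimum at 0.0027 years unless another subject's true duration is that short. The reported n counts imputed subjects as having data. Section 5.2 asks for no flag, no count of imputed values and no summary without them.

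**Step 6: after the fix.** With fully missing dates left missing, the mean rests on the n − k known durations and estimates D under the same assumption.

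**The case against.** The strongest reply is that little depends on this. Duration is not a stratification factor, an eligibility criterion or a named term in the primary model, and its summary is descriptive. That stands, and it keeps the point at the lowest level of importance.

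The trigger is also narrow, since even the year must be unknown. Protocol 5.6.1 has sites obtain the historical MRCP or ERCP used for diagnosis, so a year may often be recoverable. Protocol 5.9.2 lets MRCP serve as a diagnostic criterion and requires one at Screening, so a few subjects may truly have near-zero duration. Their dates would ordinarily be known, however, and the rule would not be needed for them. A value of 0.003 years might also be noticed in the minimum or the listing. That is possible, but nothing requires it to be marked as imputed.

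A reader might infer more than the documents support:

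- *That the bias reaches the primary model.* SAP 7.1.1 would admit relevant explanatory variables but does not name PSC duration. Protocol 8.9.2 places extra variables in additional modelling to be specified in the SAP. The route is conjecture.
- *That the bias is larger at the interim because arms hold 8 subjects.* Protocol 8.10.9 gives 8 per arm as the minimum who have completed Week 12. The baseline table uses the Randomized Set, FAS and Safety Set, which may be larger at that point.
- *That the median falls by the same proportion as the mean.* It need not, and the documents do not allow a calculation.
- *That the rule creates a false imbalance between arms.* This needs unequal missingness across arms, and the documents give no evidence of it.

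**Conclusion.** The rule is wrong as written, and the consequence is minor. It enters an unknown duration as 1 day, and at most about 0.12 years even if the first visit came a full screening window before consent. An arm's mean duration is understated by about k/n: 5%, 10% or 20% for 1, 2 or 4 of 20. These sizes rest on missingness being unrelated to duration and on assumed values of k and D. If no date is fully missing, the effect is zero. The rule can also distort the minimum, and it conceals how many durations are unknown. The effect stops at the descriptive baseline table and listing; the primary analysis, its power and its type I error rate are unchanged.

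**What to change.** In SAP 5.2, delete the rule for a date with year, month and day all missing, and remove completely missing dates from the sentence that introduces the rules. State that duration is left missing when the year of diagnosis is unknown. Report the number of subjects with data and the number missing, by arm. Keep the 1 January and first-of-month rules only where the year is known. The cost is a short text edit and one added count in the table. No new data are needed and no other analysis changes.

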5.3. Medical History

Medical history will be coded using the Medical Dictionary for Regulatory Activities (MedDRA, version 18.1 or higher). The number and percentage of subjects with any medical history will be summarized overall and for each system organ class and preferred term. Percentages will be calculated based on number of subjects in the Randomized, FAS or Safety Set, as applicable.

Subject medical history data including specific details will be presented in a listing.

5.4. Inclusion and Exclusion Criteria

Prior to randomization, the investigator will assess if the subject fulfills all of the inclusion and exclusion criteria outlined in the protocol (sections 5.1 and 5.2). The specific inclusion criterion not met or exclusion criterion which was met will be recorded in the eCRF. This information will be presented in a listing.

6. Treatments and Medications

6.1. Prior and Concomitant Medications

All medications used within 4 weeks prior to the date of screening and during the study period, as well as the reason for use, will be collected on the source documents and the CRF. Non-study medications will be classified as prior and concomitant, and coded using the current version of the World Health Organization Drug Dictionary Enhanced (WHO-DD).

Prior medications are defined as those taken at least once during the 28 days before Screening. Concomitant medications are defined as those taken at least once from 28 days prior to Screening through the EOS visit. Medications stopped in the 28 days prior to the Screening time point will not be considered concomitant.

The total number of concomitant medications and the number and percentages of subjects with at least one concomitant medication will be summarized by treatment group. The number and percentages of all concomitant medications will be summarized by treatment group, Anatomical Therapeutic Chemical (ATC) class and preferred term. Subjects who take the same medication (in terms of PT) more than once will be counted only once for that medication. All summaries will be performed using the Safety Set.

Prior medications and concomitant medications will be listed.

6.2. Study Treatments

NGM282 is provided as a sterile solution for injection in a single-use, pre-filled syringe for SC administration at doses of 1 mg and 3 mg, and volume-matched placebo. Subjects will be instructed to self-administer/dose at approximately the same time each morning over the 12-weeks treatment period. A daily study-drug administration diary is required for each subject.

Data on study-drug administration will be presented in a listing.

6.2.1. Extent of Exposure

Duration of exposure is defined as the total number of days a subject is exposed to any study drug and will be presented as the total number of days from the first dose date (Day 1) to the last dose date (date of last dose minus the date of first dose + 1) as recorded on the End of Study/Early Withdrawal page on the CRF. If the last dose date on the End of Study/Early Withdrawal page is missing, or if a subject is lost to follow-up, but the drug accountability log confirms that the subject has taken study drug, the visit date following the last completed drug accountability log will be used.

The duration of exposure to study drug by treatment will be summarized for all subjects in the Safety Set and will be presented in a table by summary statistics. The duration of exposure will then be classified into one of the following categories: <= 7 days, 8 to 14 days, 14 to 28 days, 28 to 56 days, 56 to 84 days, and >= 84 days and will be presented as the number and percentage of subjects in each duration category. Percentages will be computed from the number of subjects in the Safety Set.

A summary of each subject's exposure will be presented in a listing.

